### DOCUMENT HISTORY

Document	Date	Overall Rationale
Original Protocol	29APR2022	Not applicable
Amendment 1	06OCT2022	IB updates, eligibility clarifications, SAE reporting updates
Amendment 2	09MAY2023	Updated inclusion criteria to allow CrCl ≥45 mL/min, increased screening window to 42 days
Amendment 3	28AUG2023	Updated cycle length and dosing Schedule

#### STATEMENT OF COMPLIANCE

The trial will be conducted in accordance with International Conference on Harmonization Good Clinical Practice (ICH GCP), applicable United States (US) Code of Federal Regulations (CFR). The Principal Investigator will assure that no deviation from, or changes to the protocol will take place without prior agreement from the Investigational New Drug (IND) or Investigational Device Exemption (IDE) sponsor, funding agency and documented approval from the Institutional Review Board (IRB), except where necessary to eliminate an immediate hazard(s) to the trial participants. All personnel involved in the conduct of this study have completed Human Subjects Protection and ICH GCP Training.

The protocol, informed consent form(s), recruitment materials, and all participant materials will be submitted to the IRB for review and approval. Approval of both the protocol and the consent form must be obtained before any participant is enrolled. Any amendment to the protocol will require review and approval by the IRB before the changes are implemented to the study. All changes to the consent form will be IRB approved; a determination will be made regarding whether a new consent needs to be obtained from participants who provided consent, using a previously approved consent form.

#### ABREVIATIONS

Abbreviation	Definition/Explanation
AE	Adverse event
ALT	Alanine aminotransferase
ASCO	American Society of Clinical Oncology
AST	Aspartate aminotransferase
AV	Atrioventricular
BCVA	Best-corrected distance visual acuity
BICR	Blinded Independent Central Review
β-HCG	Beta-human chorionic gonadotropin
BID	Twice daily
BMI	Body mass index
BP	Blood pressure
BUN	Blood urea nitrogen
CBC	Complete blood count
CFR	Code of Federal Regulations
CHF	Congestive heart failure
CI	Confidence interval
CLIA	Clinical Laboratory Improvement Amendments
CLL	Chronic lymphocytic leukemia
CLcr	Creatinine clearance
Cmax	Maximum observed concentration
Cmin	Trough observed concentration
CMP	Comprehensive metabolic panel
CNS	Central nervous system
CR	Complete response
CRF	Case report form
СТ	Computed tomography
CTCAE	Common Toxicity Criteria for Adverse Events
ctDNA	Circulating tumor DNA
CYP	Cytochrome P450
CQ	Chloroquine

Abbreviation	Definition/Explanation
DILI	Drug-Induced Liver Injury
DoR	Duration of Response
DSMB	Data Safety Monitoring Board
ECOG	Eastern Cooperative Oncology Group
eCRF	Electronic case report form
ECG	Electrocardiogram
Eg	Exempli Gratia (for example)
FDA	Food and Drug Administration
GCP	Good Clinical Practice
GFR	Glomerular filtration rate
GGT	Gamma-glutamyltransferase
GI	Gastrointestinal
GMP	Good Manufacturing Practice
HBsAg	Hepatitis B surface antigen
HBV	Hepatitis B virus
HCV	Hepatitis C virus
HIV	Human immunodeficiency virus
HR	Heart rate
i.e.	Id est (that is)
IEC	Independent ethics committee
IND	Investigational New Drug
INR	International normalized ratio
IRB	Institutional review board
iwCLL	International Working Group on Chronic Lymphocytic Leukemia
LDH	Lactate dehydrogenase
MRI	Magnetic resonance imaging
NIH	National Institute of Health
PD	Pharmacodynamic(s)
PDAC	Pancreatic Ductal Adenocarcinoma
PFS	Progression-Free Survival
РК	Pharmacokinetic(s)

Abbreviation	Definition/Explanation
PO	Per os (administered by mouth)
PR	Partial response
РТ	Prothrombin time
PTT	Partial thromboplastin time
QTc	QT interval corrected
QTcF	QT interval corrected using Fredericia equation
RBC	Red blood cell
RP2D	Recommended Phase 2 Dose
SAE	Serious adverse event
SD	Stable disease
SD-OCT	Spectral-domain ocular coherence tomography
T 1/2	Terminal elimination half-life
TdP	Torsades de Pointes
T max	Time of maximum observed concentration
ULN	The upper limit of normal
VF	Visual field
WBC	White blood cell

#### 1 PROTOCOL SUMMARY

#### 1.1 Synopsis

Title:	Phase Ib/II Trial of Co mbination R P-3500 and O laparib in D NA Damage Repair Pathway D efic i ent Relapsed/Refract o ry C hronic _ymphocytic L eukemia (CORONADO CLL)							
Protocol Short Title	ORONADO CLL							
Study Description:	Open label, multi-center clinical trial to determine the safety and efficacy of combination camonsertib (RP-3500) and olaparib in DNA lamage repair pathway deficient relapsed/refractory chronic ymphocytic leukemia.							
Phase:	Ib/II							
Objectives:	Primary Objective:							
	• Phase Ib: To assess the maximum tolerated dose (MTD) and determine the recommended phase 2 dose (RP2D) of combination RP-3500 and olaparib in subjects with relapsed/refractory chronic lymphocytic leukemia with DNA damage repair deficiencies.							
	
 
Phase II: To assess the overall response rate (ORR) of combination RP-3500 and olaparib in subjects with relapsed/refractory chronic lymphocytic leukemia with DNA damage repair deficiencies.
 
							
	Secondary Objectives:							
	• To assess the safety and tolerability of RP-3500 and olaparib in the study population.							
	
 
To assess progression-free survival (PFS) in the study population
 
							
	• To assess overall survival (OS) in the study population							
	• To assess the duration of response (DoR) of the study population							
Endpoints:	Primary Endpoint:							
	
 
Phase Ib: The rate of dose-limiting toxicities (DLTs) during the DLT evaluation period.
 
Phase II: Overall response rate (ORR) will be defined by the proportion of subjects achieving any confirmed partial (PR)
 
							

	and complete remission (CR) as assessed by 2018 International Working Group on Chronic Lymphocytic Leukemia (iwCLL) response criteria.
	Secondary Endpoints:
	• The frequency of adverse events and serious adverse events characterized by type, severity (as defined by NIH CTCAE v5.0), seriousness, duration, and relationship to study treatment.
	
 
PFS as defined as the time from study drug initiation to the time documented disease progression (as assessed by 2018 iwCLL criteria) or death from any cause.
 

	
 
OS as defined as the time from registration until death from any cause.
 

	• DoR as defined as the interval of time from the date of initial documented response (PR or better as per 2018 iwCLL criteria for response) to the time of progression from the best response, the start of a new therapy, or death from any cause.
Study Population:	
 
Key Inclusion Criteria: 
 
Diagnosis of CLL according to the NCI/IWCLL criteria.
 
Repeat testing of somatic mutations and FISH analysis must be performed after progression is noted from most recent line of therapy and within 6 months of screening. Primary CLL cells must harbor at least one of these abnormalities: 
 
Somatic gene mutation testing shows mutation(s) in TP53, ATM, SF3B1, XPO1 and/or POT1,
 
Cytogenetic FISH analysis shows deletion 17p13 and/or deletion 11q22.3,
 
 
 
Relapsed or refractory after at least 2 prior lines of therapy, and in the opinion of the treating Investigator are either not eligible for other approved therapies or no approved therapies are expected to have sustained therapeutic benefit.
 
Patients in need of treatment as per iwCLL criteria.
 
Patients on BTK, PI3K or BCL2 inhibitors may enroll without meeting iwCLL criteria for treatment as long as there is clinical evidence of progression (i.e. increasing lymphocytosis, worsening anemia/thrombocytopenia attributable to CLL disease progression, increasing lymphadenopathy, or worsening patient symptoms) and require change in treatment at the discretion of the treating provider.
 

 
Absolute neutrophil count ≥1000/µL and platelet count ≥50K/µL (unless documented CLL bone marrow involvement).
 
ECOG performance status between 0-2
 
Patients must be able to receive xanthine oxidase inhibitor and/or rasburicase for tumor lysis syndrome prophylaxis.

	Key Exclusion Criteria:
	1. Patients who are currently receiving any other investigational
	

drug.

2. Prior ATR inhibitor use, but prior PARP inhibitor use for any reason is allowed on study.

	3. Evidence of active Richter's Transformation
	
 
Disease states requiring steroids (e.g. adrenal insufficiency, autoimmune conditions) are allowed as long as the steroid dose is ≤10mg of prednisone or equivalent dose of another steroid. Steroids premedications to prevent iodine contrast allergy for CT scans are allowed.
 

	
 
5. Patients who have undergone autologous stem cell transplant ≤4 weeks or allogeneic stem cell transplant ≤12 weeks prior to cycle 1 day 1 or have active graft-versus-host disease are excluded.
 
6. Patients with active known central nervous system (CNS)
 

	

involvement of CLL. Patients with a history of CNS CLL now in remission are eligible for the trial.

7. Patients with conditions significantly affect gastrointestinal function.

Study Intervention:	Camonsertib (RP-3500) PO
	Olaparib PO
Study Duration:	36 months
Participant Duration:	13 months

1.2 Schema

- Relapsed/refractory CLL after 2 prior lines of therapy and requiring treatment.
- CLL cells with at least one of the following abnormalities:
  - Somatic mutation(s) in TP53, ATM, SF3B1, XPO1 or POT1
  - Cytogenetic FISH analysis shows deletion 17p13 and/or deletion 11q23

	Phase Ib	Dose Escalat N=18-23	ion	
		RP-3500	Olaparib	
	Dose Level -1 #	40mg daily	100mg BID	
→	Dose Level 1*	50mg daily	100mg BID	
	Dose Level 2*	80mg daily	100mg BID	
	Dose Level 3*	80mg daily	150mg BID	

	Phase II Dose Expansion N=24
•	Patients enrolled at the RP2D from the phase Ib portion will also be included in the phase II analysis. At least 8 patients with deletion 11q23 and/or ATM mutation will be included.

\*Both drugs are given with intermittent dosing of 2 days per week.

#### 1.3 Schedule of Events

	Screening 	Or	-Tre	atm	Post Treatment Period							
Protocol Activities		Су	cle 1				Cycle 2		Cycle s 3 & 4	Cycle 5-18	EOT 	Follow - Up 
Day of Cycle (Visit Window)		1	2	3	8 (± 1 day)	15 (±1 day)	1 (± 2 days)	8 (± 2 days)	1 (± 3 days)	1 (± 7 days)	(+28 days)	(+14 days)
Informed Consent	Х											
Demographics	Х											
Medical History 	Х	Х										
Cancer History 	Х											
Eligibility Criteria	Х											
Registration 	Х											
Clinical Assessments						•	•			•		
Vital Signs 	Х	Х			Х	Х	Х	Х	Х	Х	Х	Х
Height/ Weight	Х	Х					Х		Х	Х	Х	Х
Physical Exam	Х	Х			Х	Х	Х	Х	Х	Х	Х	Х
ECOG Performance Status	Х	Х			Х	Х	Х	Х	Х	Х	Х	Х
ECG 	Х	Х		Х								
Adverse event collection		Со	ntinu	lous	5							
Concomitant medications	Х	Со	ntinu	Jous	5							
Laboratory Studies												
Hematology 	х	х			Х	Х	x	x	X	x	х	x
Chemistry 	х	х	х	х	Х	Х	х	х	х	х	х	х
TLS Labs 	х	х	х	х	Х	Х	х					
24 Hour Urine 	(X)	1										
Pregnancy Test 	Х	1	1	1								
HIV and Hepatitis Serologies 	х											

Day of Cycle (Visit Window)IGHV Mutational Status15XCLL FISH Analysis16XSomatic mutation testing17XPB CLL MRD by Flow Cytometry18BMA CLL MRD by Flow Cytometry19Disease AssessmentsCT ScansCT ScansXPeripheral blood immunophenotypingX		Or	n-Tre	atm	Post Treatment Period								
	Screening 	Су	cle 1				Cycle 2		Cycle s 3 & 4	Cycle 5-18 1 (± 7 days)	EOT 	Follow - Up 	
		1	2	3	8 (± 1 day)	15 (±1 day)	1 (± 2 days)	8 (± 2 days)	1 (± 3 days)		(+28 days)	(+14 days)	
IGHV Mutational Status 	Х												
CLL FISH Analysis 	Х												
Somatic mutation testing 	Х												
										X 	х		
							X 	·	·		X 		
Disease Assessments													
CT Scans	Х									X 	Х		
•	х									ACI 	х		
Bone marrow biopsy and aspirate	X 									(X) 	X 		
Correlative Studies						-			·				
Measurement of DNA damage and apoptosis 		х			х	X	x	x		x	х		
Pharmacokinetics 		Х	Х		Х	Х				X 			
PB CLL MRD by NGS 	(X)									Х	Х		
BM CLL MRD by NGS 	(X)			•			Х				Х		
Treatment Compliance													
Dispense olaparib		Х					Х		X	Х			
Dispense camonsertib (RP- 3500)		х					х		х	х			
Xanthine Oxidase Inhibitor					X 								
Dosing diary		Х					Х		Х	Х			

 A follow-up visit will occur 28 (+14) days post the last dose of study treatment. The focused history and physical should discuss residual/lingering adverse events experienced by the subject during treatment. The visit can be performed remotely should the Investigator or subject desire. For remote visits, vital signs, height/weight, and laboratory examinations are not required.

 Initial medical history at time of screening should include: baseline symptoms; a detailed history of prior cancer therapies including start and stop dates, disease progression during or after therapy, as well as discontinuations due to intolerability or any other serious illness; family and social history;.

 History of the patient's CLL course will be collected at the screening visit with special attention to prior treatment regimens (duration of therapy, best response on therapy, date of discontinuation, toxicities encountered on treatment and reason for discontinuation) and sequence.

 To register eligible subjects on study, complete a Clinical Trials Office Subject Registration Form and submit to [contact].

 Vital signs include systolic/diastolic blood pressure, heart rate, respiration rate, pulse oximetry, and body temperature.

 ECGs will be performed in triplicate at each time-point; ECG recordings should be completed approximately one minute apart. Patient must rest in supine position for at least 5 minutes prior to ECG recording. ECGs should be recorded prior to any blood draw required at the same time-point.  Hematology includes CBC with differential and platelets.

 Chemistry includes a Complete Metabolic Panel (Albumin, Alkaline Phosphatase, Aspartate Aminotransferase, Alanine Aminotransferase, Total Bilirubin, Calcium, Carbon Dioxide, Creatinine, Chloride, Glucose, Total Potassium, Protein, Sodium, and Urea Nitrogen).

 Tumor lysis syndrome (TLS) labs: lactate dehydrogenase, phosphorus, and uric acid

 Optional and can be performed to calculate creatinine clearance instead of the estimated creatinine clearance through Cockroft-Gault equation.

 Pregnancy test (serum or urine) must be obtained at screening  $\leq$  3 days prior to C1D1 for all women of childbearing potential and as clinically indicated while on treatment.

 Must be conducted within 6 months of registration.

 If the subject has had successful testing in the past, this will be accepted and repeat *IGHV* mutational status will not be required.

 Should be performed after progression is noted from most recent line of therapy and within 6 months of screening and should include deletion 13q14, trisomy 12, deletion 11q22.3, deletion 17p13.

<sup>1 Screening procedures must be completed  $\leq$  42 days prior to C1D1 unless noted otherwise.

<sup>2 The end of treatment visit should occur when the patient discontinues treatment *for any reason*. This may be due but not limited to unacceptable toxicity from the combination therapy, patient/treating physician preference, progressive disease or completion of 18 cycles of combination therapy (whichever comes first). If this visit overlaps with a regularly scheduled visit, only the procedures listed in the calendar for the EOT visit will be performed. All end of treatment procedures should be completed  $\leq$  28 days after discontinuation of treatment.

 Should be performed after progression is noted from most recent line of therapy and within 6 months of screening. At a minimum, the following somatic mutations must be tested: *TP53, ATM, SF3B1, POT1* and *XPO1*. While not required, the following genes are strongly encouraged to be tested as well: *NOTCH1, BIRC3, BRAF, KRAS, DDX3X, MYD88 and CXCR4*.

 CLL MRD testing by flow cytometry should be performed on peripheral blood on C5D1, C9D1 and EOT.

 BM MRD testing by flow cytometry through a local lab should be performed on any BM aspirate obtained after screening. An additional aspirate sample should be collected and processed for correlative studies.

 At C5D1 (±7 days): CT scans of the neck, chest, abdomen and pelvis should be performed with contrast agents unless contraindicated for medical reasons. Should this CT show that the patient has achieved an iwCLL 2018 defined complete remission and absolute lymphocyte count is <4000, then a bone marrow biopsy should be performed at this time to confirm the complete remission. At any other study time point beyond C5D1 (excluding end of treatment): If patient achieves hematologic recovery or the treating physician suspects the patient has achieved a complete remission per the 2018 iwCLL criteria, then a peripheral blood immunophenotype should be ordered. Should this show no evidence of circulating CLL cells, then a complete remission can be confirmed with CTs of the neck, chest, abdomen and pelvis along with a bone marrow biopsy. If CTs and bone marrow biopsy are indicated, studies need to be performed within 28 days.

 If subject achieves hematologic recovery or the treating physician suspects the patient has achieved a complete remission as per the 2018 iwCLL criteria, then a peripheral blood immunophenotype should be ordered. Please refer to reference **20** for sequencing of testing to confirm a complete remission.

 The bone marrow biopsy performed at screening should be after progression is noted from most recent line of therapy and within 6 months of screening. If a bone marrow biopsy is not performed at screening, an archival tissue maybe requested at the discretion of the PI. BM CLL MRD by NGS should be performed on any BM aspirate obtained after screening.

 Should peripheral blood immunophenotying show no evidence of circulating CLL cells, then a complete remission can be confirmed with CTs of the neck, chest, abdomen and pelvis and a bone marrow biopsy. Please refer to reference **20** for sequencing of testing to confirm a complete remission.

 BMBx at screening and EOT are the only ones required on study. If a prior bone marrow biopsy showed the patient to be in a complete remission, a repeat bone marrow biopsy is not required unless progression of disease is suspected.

 Samples should be collected prior to dosing of the drugs. Samples should be collected on C1D1, C1D8, C1D15, C2D1, C2D8 and at time of progression.

 Refer to section **1.5.1** for time points

 PB CLL MRD by NGS should be performed on peripheral blood on C5D1, C9D1 and EOT as tracking samples..

 The treating physician may choose to collect the identification sample for MRD by NGS on either the PB or BM at screening depending on which compartment has CLL cells present. Thus, two samples (one from PB and one from BM) for MRD by NGS at screening are not required.

 Xanthine oxidase inhibitor agent must be given at least 72 hours prior to C1D1 and during the first cycle of study therapy.

#### 1.4 Long Term Follow -Up

Activities 	Year 1	Year 2-5 	Year 6-10 
Office visit for history and physical 	Every 3 months (±14 days)	Every 3-6 months (±14 days)	Every 3-12 months (±28 days)
Labs 	Every 3 months (±14 days)	Every 3-6 months (±14 days)	Every 3-12 months (±28 days)

<sup>1 Long term follow-up is calculated from the last date that the patient took any study drug.

<sup>2 Follow up length in years 2-10 is at the discretion of the treating physician.

<sup>3 An abbreviated history and physical can be performed, but should include signs or symptoms of CLL relapse or disease progression. This includes B-symptoms (fevers, drenching night sweats, unintentional weight loss), new palpable lymphadenopathy and/or hepatosplenomegaly, new or progressive symptoms from the patient's last visit.

<sup>4 Hematology includes CBC with differential and platelets. Chemistry includes a Complete Metabolic Panel (Albumin, Alkaline Phosphatase, Aspartate Aminotransferase, Alanine Aminotransferase, Total Bilirubin, Calcium, Carbon Dioxide, Creatinine, Chloride, Glucose, Total Potassium, Protein, Sodium, and Urea Nitrogen).

#### 1.5 Correlative Study Calendar

#### 1.5.1 Pharmacokinetic

Cycle 1		Day 1						Day 8 (±1 day)				Day 15 (±1 day)						
Time of Collection (hours after drug dosing)	Pre	0.5	1	2	4	24	Pre	Pre	0.5	1	2	4	Pre	0.5	1	2	4	24
Time Window for Collection (min)		±5	±10	±15	±15	±120			±5	±10	±15	±15		±5	±10	±15	±15	±120
PK Blood Draw	х	х	х	Х	Х	х		Х	х	Х	Х	Х	Х	х	Х	Х	Х	х
ECG 				х			Х											

Cycle 5	Day 1				
Time of Collection (hours after drug dosing)	Pre	0.5	1	2	
Time Window for Collection (min)		±5	±10	±15	
PK Blood Draw	х	х	х	х	

<sup>1 ECGs will be performed in triplicate at each time-point; ECG recordings should be completed approximately one minute apart. Patient must rest in supine position for at least 5 minutes prior to ECG recording. ECGs should be recorded prior to any blood draw required at the same time-point.

#### 2 OBJECTIVES AND ENDPOINTS

#### 2.1 Primary Objective

2.1.1 Phase Ib: To assess the maximum tolerated dose (MTD) and determine the recommended phase 2 dose (RP2D) of combination RP-3500 and olaparib in subjects with relapsed/refractory chronic lymphocytic leukemia with DNA damage repair deficiencies.

Primary endpoint: The rate of dose-limiting toxicities (DLTs) during the DLT evaluation period.

2.1.2 Phase II: To assess the overall response rate (ORR) of combination RP-3500 and olaparib in subjects with relapsed/refractory chronic lymphocytic leukemia with DNA damage repair deficiencies.

Primary endpoint: Overall response rate (ORR) will be defined by the proportion of subjects achieving any confirmed partial (PR) and complete response (CR) as assessed by 2018 International Working Group on Chronic Lymphocytic Leukemia (iwCLL) response criteria.

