# 7.4.2 Disease Assessment Algorithm

All patients should have a CT scan of the neck, chest, abdomen, and pelvis with IV contrast at the time of screening or up to 28 days prior to C1D1. CTs are required at C4D1 (± 7 days). Should this CT show that the patient has achieved an iwCLL 2018 defined complete remission (CR) and absolute lymphocyte count is <4000, then a bone marrow biopsy should be performed to confirm CR.

At any other study time point beyond C4D1 excluding end of treatment, the patient may have a disease assessment if the subject achieves hematologic recovery or the treating physician suspects the patient has achieved a CR as per the 2018 iwCLL criteria. At that time, a peripheral blood immunophenotype should be ordered. If the peripheral blood

immunophenotype shows no evidence of circulating CLL cells, then CTs of the neck, chest, abdomen, and pelvis should be performed. Should the CT also confirm CR, then a bone marrow biopsy should be performed to confirm CR. The study team has 28 days to complete all necessary testing required to confirm a CR from the time a CR is suspected by the treating physician. During this time, protocol treatment may continue as prescribed.

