# 7.5.2 Partial Remission (PR)

PR is defined by achieving at least 2 of the criteria described in Sections 7.4.1a, 7.4.1b, or 7.4.1c (if abnormal before therapy), as well as one or more of the features listed in section 7.2d. If only 1 parameter in Sections 7.4.1a, 7.4.1b, 7.4.1c, 7.4.1d were abnormal before therapy, only 1 needs to improve.

- A decrease in the number of blood lymphocytes to 50% or less from the value recorded immediately prior to initial dose of therapy.
- Reduction in lymphadenopathy compared with baseline by palpation as defined by the following: (Additional assessment of response by CT scan of abdomen, pelvis, and thorax should be performed per study calendar.):
  - A decrease in lymph node size by 50% or more either in the sum of the longest diameters of the enlarged lymph node(s) selected at baseline as assessed by physical examination (an established number has been a maximum of 6) or the sum products of the same enlarged lymph nodes selected at baseline as assessed by imaging (an established number in clinical trials of lymph nodes has been up to 6).
  - No increase in any lymph node, and no new enlarged lymph node. In small lymph nodes (longest diameter < 1.5 cm), an increase <25% is not considered significant.
- A regression ≥ 50% of the extent of enlargement of the spleen below the costal margin defined by palpation, or normalization in size. When assessed by CT, scan spleen size

must have regressed by  $\geq$  50% in length beyond normal. A persistence of splenomegaly posttherapy may have limited influence on outcome in CLL.

- A regression of ≥ 50% of the extent of enlargement of the liver below the costal margin defined by palpation, or normalization in size. Given the impact of numerous medical conditions, liver size by physical examination or CT scan is not a reliable measure of hepatic involvement by CLL and should only be counted if hepatomegaly is clearly attributable to lymphoid involvement.
- The blood count should show one of the following results:
  - Platelet counts greater than 100 × 109/L (100,000/mcL) or 50% improvement over baseline.
  - Hemoglobin greater than 110 g/L (11.0 g/dL) or 50% improvement over baseline without requiring red blood cell transfusions

Patients who achieve a CR as per section 7.5.1 but bone marrow examination shows residual lymphoid nodules deemed related to CLL residual disease will be labeled as having achieved a nodular partial remission (nPR).

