# 9.4.2 Overall Response Rate

Overall response rate (ORR) will be calculated as the sum of subjects achieving any complete response (including CR and CRi) or any partial response (including PR and nPR) divided by the total number of response evaluable subjects. Subjects without a baseline/screening tumor assessment or at least one on-treatment assessment will be considered non-responders. Each value will be reported along with a one-sided 95% exact binomial confidence interval. No hypothesis testing will be performed for ORR.

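### The phase II primary endpoint counts confirmed responses in Sections 1.1 and 2.1.2 but any response in Section 9.4.2, and no assessment is designated or timed to confirm a PR

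*Combined protocol and SAP*

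**What the plan says.** **Endpoint.** Section 2.1.2 defines ORR as the "proportion of subjects achieving any confirmed partial (PR) and complete response (CR) as assessed by 2018 International Working Group" criteria, and the Synopsis (1.1) also requires confirmation.

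**Analysis.** Section 9.4.2 computes ORR from the patients with "any complete response (including CR and CRi) or any partial response (including PR and nPR) divided by the total number of response evaluable subjects". The word *confirmed* is absent, and CRi and nPR, which 1.1 and 2.1.2 do not mention, are named. On missing data it adds: "Subjects without a baseline/screening tumor assessment or at least one on-treatment assessment will be considered non-responders".

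**Confirming a response.** Only CR has a procedure. After the fixed on-treatment CT, hematologic recovery or a suspected CR leads first to a blood immunophenotype. Footnote 20 of the Schedule of Events (1.3) continues: "Should this show no evidence of circulating CLL cells, then a complete remission can be confirmed with CTs", together with a marrow biopsy. Section 7.4.2 follows the same order: if the "immunophenotype shows no evidence of circulating CLL cells, then CTs of the neck, chest, abdomen, and pelvis should be performed". Section 7.4.2 allows 28 days to complete this work-up.

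**PR.** Section 7.5.2 sets thresholds against baseline and gives no repeat assessment or minimum duration. Its nodal criterion can be judged clinically: "Reduction in lymphadenopathy compared with baseline by palpation as defined by the following". CT is additional, per the calendar.

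**Fixed CT.** Footnote 20 places it at C5D1; Section 7.4.2 places it at C4D1.

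**The concern.** ORR is the phase II primary endpoint in an open-label, single-arm cohort of 24. With no hypothesis test, the estimate and its one-sided bound are the result. If *confirmed* means seen again, a PR observed once and then lost is a non-response under 2.1.2 and a response under 9.4.2. Nothing in Sections 7.4 or 7.5 says what would confirm a PR, when, or how to count one with no later qualifying assessment. An analyst could choose between the readings after seeing the responses, and the chosen figure would then be read against a 60% target.

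**Working it through.** **1. Reproduce Table 19.** Inputs from Section 9.1.1: n = 24, exact one-sided 95% Clopper-Pearson. The lower bound L for x responders solves P(X ≥ x | 24, L) = 0.05, which is the 0.05 quantile of Beta(x, 24 − x + 1). For x = 10 to 18 this gives 24.6, 28.2, 31.9, 35.8, 39.7, 43.7, 47.9, 52.1 and 56.5%. Table 19 prints 24, 28, 31, 35, 39, 43, 47, 52 and 56%, which are the same values truncated. The table is sound.

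**2. Effect of each PR on which the definitions disagree.** One patient is 1/24 = 4.2 points. The documents give no share of PRs that would fail confirmation, so the range below is assumed. It starts from 15 responders of any kind.

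| PRs not confirmed (assumed) | Responders counted | ORR | Lower bound |
|---|---|---|---|
| 0 | 15/24 | 62.5% | 43.7% |
| 1 | 14/24 | 58.3% | 39.7% |
| 2 | 13/24 | 54.2% | 35.8% |
| 3 | 12/24 | 50.0% | 31.9% |
| 4 | 11/24 | 45.8% | 28.2% |
| 5 | 10/24 | 41.7% | 24.6% |

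Each step lowers the bound by 3.6 to 4.0 points. Since 0.60 × 24 = 14.4, the smallest count reaching the target is 15, so from there one disputed PR takes the estimate below 60%. With no disputed PR the two ORRs are identical.

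**3. Timing of CT.** With 21-day cycles (Section 6.1):
- C5D1 = 4 × 21 + 1 = day 85, and C4D1 = 3 × 21 + 1 = day 64.
- C18D21 = 18 × 21 = day 378, when Section 4.5.1 requires the end-of-treatment assessments, including imaging.
- The gap from C5D1 is 378 − 85 = 293 days, or 41.9 weeks. From C4D1 it is 378 − 64 = 314 days, or 44.9 weeks.

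This is the longest gap to the next required CT during the 18 cycles. A patient who stops earlier has the end-of-treatment CT earlier. An intermediate CT needs hematologic recovery or suspected CR, and then no circulating CLL cells. A PR allows lymphocytes at up to half the pre-treatment value (7.5.2), so a patient in PR may not qualify.

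**4. What the schedule does offer.** Physical examination and hematology fall on Day 1 of every cycle through 18 (1.3). CT is scheduled at end of treatment whatever the reason for stopping. Patients who stop without progression continue disease assessments (6.9.4), although the long-term calendar (1.4) lists only history, examination and laboratory tests. Assessments therefore exist, but none is assigned to PR confirmation.

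**The case against.** The best reply is that *confirmed* may mean no more than documented by iwCLL criteria. Section 6.9.1 speaks of confirmed progression although Section 7.5.3 asks for no repeat, and 7.5.3 itself has nodal progression confirmed by physical examination. In 9.4.2 the word *any* introduces response categories, and the sentence about one on-treatment assessment is a missing-data rule. On that reading the sections agree about confirmation. The cited iwCLL criteria, incorporated by reference, might also set a duration; they are not available here.

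This reading is possible but not secure. Sections 2.2.2 and 2.2.4 use *documented* for progression and first response, so a different word in 2.1.2 suggests a different meaning. Where the protocol spells out how a response is confirmed, it requires further testing.

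Three stronger inferences are tempting, and the documents do not support them:

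- **That the schedule cannot confirm a PR.** The Day 1 examination and blood count, the palpation-based nodal criterion, and the end-of-treatment CT in patients stopping without progression could each contribute.
- **That the same patients must give two ORRs.** They differ only if confirmation means a repeat assessment and at least one PR is not seen again.
- **That the confirmed definition would discard most PRs.** No rate is given, and a loss of five out of 15 is only the far end of an assumed range.

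It is also fair that no test, power figure or go/no-go cut-off depends on ORR, which limits the consequence to the reported estimate and how it is read.

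**Conclusion.** The inconsistency stands. The primary endpoint requires confirmation in 1.1 and 2.1.2 but not in 9.4.2, the categories named differ (CRi and nPR), and PR confirmation has no method, interval or designated visit. The two definitions can give different ORRs, by 4.2 points in the estimate and about 4 points in the lower bound for each PR on which they disagree. The total cannot be derived from the documents and may be zero.

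The size rests on n = 24, on *confirmed* meaning a repeat assessment, and, for the bound, on 10 to 15 responders. Because one patient can move the estimate across 60%, the definition should be settled before responses are summarised.

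**What to change.** Use one ORR definition in 1.1, 2.1.2 and 9.4.2, and state in each whether CRi and nPR count. Then either:

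- **Any response:** delete *confirmed* from 1.1 and 2.1.2 and label the ORR as unconfirmed; or
- **Confirmed response:** keep the word and add it to 9.4.2. Define PR or nPR as confirmed when the 7.5.2 criteria are still met, without progression, on a scheduled Day 1 examination and blood count at a pre-stated minimum interval after first documentation. Take the interval from the cited iwCLL criteria if they set one; otherwise the sponsor must choose and state it. Say how a PR with no later qualifying visit is counted. Leave CR confirmation by CT and marrow as in 7.4.2, and report the unconfirmed ORR as a sensitivity result.

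Under either option, reconcile the fixed CT between C5D1 (1.3) and C4D1 (7.4.2).

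The cost is wording: no new visit or scan, and no change to N = 24 or Table 19. Under the second option the reported ORR may be somewhat lower.
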